10.2.4 Muscle Biopsy

Upon qualification for the study based on Screening and Baseline assessments, all subjects will undergo two muscle biopsies at Baseline and Week 48.

The Baseline muscle biopsy may be obtained as soon as eligibility is confirmed (i.e. Baseline assessment is complete and genotype is confirmed), prior to the first dose of study treatment. The first dose of study treatment must be within 4 weeks of the Baseline Functional Assessment visit. Muscle biopsy surgery must be performed within the 4-week window between the Baseline Functional Assessment visit and Week 1. Subjects will not begin to receive study treatment until after the Baseline muscle biopsy has been performed.

The Baseline muscle biopsy will be obtained from one gastrocnemius muscle and the subsequent muscle biopsy will be obtained from the contralateral muscle. A previously unbiopsied alternative upper leg muscle may be used if the gastrocnemius has been biopsied previously. If an alternative muscle is used, the same contralateral muscle will be biopsied at the subsequent muscle biopsy.

The Biopsy at Week 48 must occur within 2 weeks after the week 48 visit and at least 48 hours after the most recent infusion.

All analyses related to quantification of dystrophin protein will be performed at the conclusion of the study.

Tissue samples may be stored for a maximum of 15 years and may be used for research at a later time (Long term follow-up).

10.2.4.1 RNAseq Analysis

The efficiency of splicing alteration will be assessed by RNA Sequencing (RNA-Seq). Data will be analyzed to establish *DMD* mRNA copy number, and the exon-exon junction frequency quantified, with normalization to exon junction read values from exon junctions in regions distinct from the targeted exon.

10.3 **Additional Assessments**

10.3.1 Genotype Confirmation

If a subject does not have a previously acceptable genetic report stating their mutation, blood will be collected to send out for genetic mutation analysis of *DMD*.

11 ADVERSE EVENTS AND SAFETY REPORTING

11.1 Collection of Adverse Events

Over the entire duration of the study, site personnel will ensure that all AEs are recorded appropriately. If an AE occurs, the primary concern is for subject safety, and the Investigator will use his/her judgment and expertise to determine the appropriate course of action.

All AEs from the time of informed consent through the End of Study visit (or early termination from the study) will be recorded in each individual subject's CRF. For subjects who prematurely discontinue the study (see Section 7.5), AEs will continue to be recorded until 28 days after the last study treatment infusion.

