	
 ○ Forced vital capacity, as measured in absolute values and by % predicted forced vital capacity (FVC%) in patients \geq age 10. ○ [REDACTED] ○ [REDACTED] 
 • [REDACTED] • Adult PROMIS Upper Extremity Report for patients 18+ years. • Immune staining may be performed on biopsy specimens for members of the dystrophin-associated protein complex, such as the sarcoglycans, dystroglycans and n-Nos. • [REDACTED]

Methodology
	
This is a open-label, 48-week study to evaluate the efficacy and safety of three phosphorodiamidate morpholino oligomers (PMOs) (casimersen, eteplirsen, and golodirsen) in 6 subjects with genotypically confirmed Duchenne muscular dystrophy (DMD) with duplication mutations amenable to correction by skipping exon 45, 51, or 53, respectively.
 
Subjects will be evaluated for inclusion during a screening period of approximately 8 weeks. Eligible subjects who have out-of-frame duplications of a single exon that may be corrected by skipping exon 45, 51, or 53 will receive once weekly intravenous (IV) infusions of 30 mg/kg casimersen, 30 mg/kg eteplirsen, or 30 mg/kg golodirsen respectively for 48 weeks.
 
Upon qualification for the study based on Screening and Baseline assessments, all subjects will undergo a muscle biopsy for baseline assessment of dystrophin expression. All subjects will undergo a second biopsy at 48 weeks of treatment..
 
Efficacy, including the Bayley scale, NSAA, 100M, ACTIVE-seated and pulmonary function tests, will be assessed at regularly scheduled (12 week intervals) study visits and safety will be monitored on an ongoing basis for all subjects.
 
Safety will be assessed through the collection of adverse events (AEs), serious adverse events (SAEs), deaths, discontinuation of study due to AEs, laboratory tests, electrocardiograms (ECGs), echocardiograms (ECHOs), vital signs, physical examinations throughout the study as described in the Schedule of Events (see Sections 9 and 10).

Duration of Study
	
The total duration of the study will be up to 60 weeks based on the three parts below:
 
 • Screening/Baseline Period: Approximately 8 weeks • Treatment Period: Up to 48 weeks

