	
 • Safety Follow-up: Subjects will be followed up with by phone call approximately 4 weeks (28 days) following last infusion to check for adverse events or other significant findings.
Number of Subjects	Approximately 6 subjects will be included in this study, to be enrolled by invitation.

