Post-treatment Follow-up/Clinical Transition Period	
Subjects will be followed up with by phone call approximately 4 weeks (28 days) following last infusion to check for adverse events or other significant findings.
 
At the conclusion of the 48 week study period, subjects will be enrolled in the Sarepta Clinical Transition Program and will be followed clinically in the NCH DMD clinic for safety, specifically for monitoring of renal function as per the prescribing information for casimersen and golodirsen. All prescribing recommended testing will be performed for clinically monitoring only. Those subjects receiving golodirsen or casimersen via this program will be monitored by urine dipstick every month, and serum cystatin C and urine protein to creatinine ratio (UPCR) every 3 months. There is no additional clinical safety testing recommended per the prescribing information for eteplirsen.- Additionally, through this program the subjects will be provided uninterrupted weekly drug access after conclusion of the 48 week study period. Subjects will remain on the Clinical Transition Program/SareptaAssist until study samples can be analyzed and insurance authorization for the drug(s) can be obtained, or the efficacy of the drug is determined to not meet the standards for continuation. The threshold for study drug continuation in Sarepta's Clinical Transition Program/SareptaAssist is a 10 percent increase in dystrophin positive fibers (defined as fibers with 30 percent of the circumference positive for dystrophin) as determined by immunofluorescence staining of the baseline and 48-week post-treatment muscle biopsies. Subjects will receive weekly drug infusions via home health care arranged by Sarepta Therapeutics and as noted above will be monitored clinically in the NCH DMD clinic.

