6 INVESTIGATIONAL PLAN

6.1 Overall Study Design

This is a open label, 48-week study to evaluate the efficacy and safety of three PMOs – casimersen, eteplirsen, and golodirsen – in 6 subjects with genotypically confirmed *DMD* with duplication mutations amenable to correction by skipping exon 45, 51, and 53, respectively.

Subjects will be evaluated for inclusion during a Screening period of approximately 8 weeks. Eligible subjects who have out-of-frame duplications of a single exon that may be corrected by skipping exon 45, 51, or 53 will receive once weekly intravenous (IV) infusions of 30 mg/kg casimersen, 30 mg/kg eteplirsen, or 30 mg/kg golodirsen respectively for 48 weeks.

Upon qualification for the study based on Screening and Baseline assessments, all subjects will undergo a muscle biopsy for baseline assessment of dystrophin expression. All subjects will undergo a second biopsy at 48 weeks of treatment.

Efficacy will be assessed at regularly scheduled (12 week intervals) study visits and safety will be monitored on an ongoing basis for all subjects.

Safety will be assessed through the collection of adverse events (AEs), laboratory tests, electrocardiograms (ECGs), echocardiograms (ECHOs), vital signs, and physical examinations throughout the study as described in the Schedule of Events (Table 6). A Safety Follow Up phone call will be placed approximately 4 weeks (28 days) after the last study infusion to check for new adverse events, to obtain any new information regarding ongoing AEs and/or any other noteworthy subject progress.

At the conclusion of the 48 week study period, subjects will be enrolled in the Sarepta Clinical Transition Program via the SareptAssist patient support program. Subjects will be followed clinically in the NCH DMD clinic for safety, specifically for monitoring of renal function as per the prescribing information for casimersen and golodirsen. All prescribing recommended testing will be performed for clinical monitoring only. Those subjects receiving golodirsen or casimersen via this program will be monitored by urine dipstick every month, and serum cystatin C and urine protein to creatinine ratio (UPCR) every three months. There is no additional clinical safety testing recommended per the prescribing information for eteplirsen.

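### For completers, 11.1 stops CRF recording of AEs at the End of Study visit, but the synopsis, 6.1 and 13.1 plan and report a 28-day safety call that Section 9 and Table 6 omit

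*Combined protocol and SAP*

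**What the plan says.** Section 11.1 opens with a broad duty: "Over the entire duration of the study, site personnel will ensure that all AEs are recorded appropriately". Its second paragraph then sets the CRF window: "All AEs from the time of informed consent through the End of Study visit (or early termination from the study) will be recorded" in the CRF. The only extension is for early leavers: "For subjects who prematurely discontinue the study (see Section 7.5), AEs will continue to be recorded until 28 days after" the last infusion.

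Other sections describe a later contact:

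- **Synopsis, Duration of Study:** "The total duration of the study will be up to 60 weeks based on the three parts below". The parts are screening and baseline (about 8 weeks), treatment (at most 48 weeks) and a safety follow-up, for which "Subjects will be followed up with by phone call approximately 4 weeks (28 days) following last infusion".
- **Synopsis, Post-treatment Follow-up:** the call is repeated with its purpose: "Subjects will be followed up with by phone call approximately 4 weeks (28 days) following last infusion to check for adverse events".
- **6.1:** "A Safety Follow Up phone call will be placed approximately 4 weeks (28 days) after the last study infusion". One of its stated aims is "to obtain any new information regarding ongoing AEs".
- **13.1:** the final report includes data through this call.

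The remaining passages point both ways:

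- **11.4** records AEs and SAEs up to a last follow-up visit, a term the protocol does not define. It stops following AEs at the earliest of resolution, the end of the subject's participation, or study termination. SAEs are followed until they resolve, stabilise or return to baseline.
- **7.4** ends participation at the Week 48 visit, yet gives its maximum length as 60 weeks.
- **10.1.6** takes the AE collection times from Section 9. The last visit there is 9.8 (Week 48 or early termination). Table 6 ends at the same column, and none of its footnotes mentions a call.

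**The concern.** The plan intends to report AE data from a contact that falls outside its own specific recording rule for completers and outside its visit schedule. Stating the 28 days for early leavers alone invites the inference that completers do not have them.

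Safety and tolerability is a primary objective (5.1). Its analysis is descriptive (14.3.2) in about six subjects, so one unrecorded event can change a table. Completers receive their last study infusion at Week 48 and have a second open muscle biopsy after it. If staff apply the cut-off sentence in 11.1, non-serious events after that infusion and biopsy may not reach the CRF, although 11.3.2 asks for every AE to be classified by its relationship to study procedures. Early leavers would meanwhile be observed for the full 28 days, so the two groups would have unequal follow-up.

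**Working it through.** **Step 1. Reproduce the stated duration.** Inputs from the synopsis are screening and baseline of about 8 weeks, treatment of at most 48 weeks, and the call about 4 weeks after the last infusion.

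- With the call: 8 + 48 + 4 = 60 weeks, the stated figure.
- Without the call: 8 + 48 = 56 weeks.
- Without the call but with the latest permitted biopsy (2 weeks after the Week 48 visit): 56 + 2 = 58 weeks.

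The figure of 60 is matched only when the call period is counted. Section 7.4 gives the same 60 weeks while ending participation at Week 48. It therefore conflicts with itself, and its number supports the call.

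**Step 2. Set the timeline for a completer.** Take the Week 48 infusion (9.8.1) as day 0 and as the last study infusion. By 9.8.2 the biopsy is at least 48 hours after the most recent infusion and within 2 weeks of the visit, so it falls on day 2 to day 14. The call falls on about day 28.

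**Step 3. Shortfall under each reading.** Shortfall = 28 minus the day on which CRF recording ends.

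| Reading | Recording ends | Shortfall per completer |
|---|---|---|
| The call counts (synopsis, 6.1, 13.1, opening of 11.1) | about day 28 | 28 - 28 = 0 days |
| 11.1 cut-off, Day 2 biopsy counted in the visit | day 2 to 14 | 28 - 14 = 14 to 28 - 2 = 26 days |
| 11.1 cut-off, visit ends with Day 1 | day 0 | 28 - 0 = 28 days |

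If all six subjects complete, the post-infusion window is 6 x 28 = 168 subject-days. The totals not recorded are then 0, or 6 x 14 = 84 to 6 x 26 = 156, or 6 x 28 = 168. Under the last two readings recording ends no later than the biopsy day. The 28-day window would add 14 to 26 days after the biopsy.

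**Step 4. Does another section settle it?**

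- 11.4 could include the call, but its end point is undefined and the call is not a scheduled visit. Its stopping rule for ongoing AEs depends on when participation ends, which 7.4 answers in two ways.
- 10.1.6 sends staff to Section 9, where the call does not appear.
- For SAEs, 11.4 follows events to resolution or stability, and 11.5 requires reporting of those that occur after the trial. Neither provision covers new non-serious events.

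**The case against.** The strongest case on the other side is that the intent is clear and the rest is drafting. The opening of 11.1 covers the whole study, and by the 60-week count the study includes the call. The call is the only post-treatment study contact described, so the last follow-up visit in 11.4 most naturally means that call. Section 13.1 presupposes that its data are recorded. The trial has one centre, where a misreading is easily corrected.

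Much of this stands. It makes the 28-day reading the better supported one, and under it nothing is lost. It does not remove the conflict: the one sentence that sets the CRF window for completers says otherwise, and the schedule that staff work from omits the call.

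Three stronger inferences should be resisted.

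- A reader might infer that half or more of the post-infusion window is lost. That holds only under the 11.1 cut-off, the less supported reading, so the range starts at 0.
- A reader might take 7.4 as placing the end of participation firmly before the call. Its 60 weeks point the other way.
- Because 6.1 continues weekly drug access through the transition programme, a reader might infer that the extra days are worthless unless later events stay in the treatment-emergent tables. The documents do not support this. They give neither a date for the first transition infusion nor an end date for treatment-emergent events. Relationship to procedures is classified separately (11.3.2), and non-emergent events are listed (11.3.9), so recorded events are kept either way.

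**Conclusion.** The inconsistency is real and worth correcting, but its effect is conditional. The shortfall in CRF recording of non-serious AEs is 0 days per completer if the call counts, 14 to 26 days under the 11.1 cut-off with the biopsy counted in the visit, and 28 days if the visit ends with Day 1. The documents do not show that any event will be lost, or that SAE follow-up and reporting are deficient.

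The figures assume that the Week 48 infusion is the last study infusion, that the biopsy falls within its stated window, and that the call takes place at about 28 days. The subject-day totals also assume that all six subjects complete. The primary efficacy analysis is not affected.

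**What to change.** Reconcile 11.1, 11.4 and 7.4 with 6.1 and 13.1:

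- State one AE recording window for every treated subject, from consent through the planned safety call about 28 days after the last study infusion.
- In 11.4, replace the undefined last follow-up visit with that end point, and let follow-up of ongoing AEs run to the call.
- In 7.4, make the end of participation agree with the 60 weeks it already gives.
- Add the call to Section 9 and to Table 6, so that 10.1.6 leads staff to it.

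Recording the date of the first transition-programme infusion, so that later events can be identified, is optional. No change to the treatment-emergent tables is needed to resolve the conflict.

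The cost is wording changes and CRF instructions for the call. The call is already planned, so no new contact or procedure is required.

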11.2 Definition of Adverse Events

11.2.1 Adverse Event (AE)

An AE is any untoward medical occurrence in a clinical trial participant, which does not necessarily have a causal relationship with the investigational drug. An AE can, therefore, be any unfavorable and unintended symptom, sign, disease, condition, or test abnormality that occurs during or after administration of an IP whether or not considered related to the IP. Adverse events include:

- Symptoms described by the subject or signs observed by the Investigator or medical staff.
- Test abnormalities (laboratory tests, ECG, X-rays, etc.) that result in an alteration in medical care (diagnostic or therapeutic).

Abnormalities present at Screening are considered AEs only if they reoccur after resolution or worsen during the AE collection period.

11.2.2 Serious Adverse Event (SAE)

An SAE is defined as any AE that results in any of the following:

- **Death:** The subject died as the result of the event.
- **Life-threatening event:** Any AE that places the subject, in the view of the Sponsor-Investigator, at immediate risk of death from the AE as it occurred, i.e., does not include an AE that had it occurred in a more severe form, might have caused death.
- **Required or prolonged insubject hospitalization:** The AE resulted in hospitalization or prolonged an existing hospitalization. Since hospitalization may be part of the study, only hospitalizations that are longer than expected based on Investigator judgment, will be considered prolonged hospitalizations.
- **Persistent or significant disability/incapacity:** An AE that results in a substantial disruption of a person's ability to conduct normal life functions.

- **Congenital anomaly/birth defect:** A congenital anomaly/birth defect that occurs in the offspring of a subject exposed to the IP.
- **Important medical events:** An AE that may not result in death, be life-threatening, or require hospitalization may be considered an SAE when, based upon appropriate medical judgment, the event may jeopardize the subject and may require medical or surgical intervention to prevent one of the outcomes listed above.

11.3 Classification of Adverse Events

Each AE whether serious or non-serious will be classified by the Investigator according to the following rules and definitions.

11.3.1 Relationship to Investigational Product

For each AE, the Investigator will determine whether there is a reasonable likelihood that the AE may have been caused by the study treatment according to the categories below:

Unrelated:	The event is clearly not related to the study treatment
Possibly/probably related:	The event could be related/is likely to be related to the study treatment
Definitely related:	The event is clearly related to the study treatment

11.3.2 Relationship to Study Procedures

For each AE the Investigator will determine whether there is a reasonable possibility that the AE may have been caused by the study procedures according to the categories below:

Unrelated:	The event is clearly not related to the study procedures
Possibly/probably related:	The event could be related/is likely to be related to study procedures
Definitely related:	The event is clearly related to the study procedures

11.3.3 Relationship to Underlying Disease

For each AE the Investigator will determine whether there is a reasonable possibility that the AE may be related to the underlying disease according to the categories below:

Unrelated:	The event is clearly not related to the underlying disease
Possibly/probably related:	The event could be related/is likely to be related to the underlying disease

Definitely related: The event is clearly related to the underlying disease

Events of disease progression may be considered AEs, based on the Investigator's discretion.

11.3.4 Severity of Adverse Events

Note that severity is not the same as "seriousness," which is defined in Section 11.2.2 and which serves as a guide for defining regulatory reporting obligations.

The Investigator will assess the severity of all AEs as Mild, Moderate, or Severe, based on the following definitions:

Mild: The event does not interfere with the subject's usual activities.

Moderate: The event interferes with the subject's usual activities.

Severe: The event prevents the subject from undertaking their usual activities and requires therapeutic intervention or cessation of the study treatment.

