The non-clinical safety profiles of casimersen and golodirsen are similar to other PMOs tested to date; no cardiovascular, respiratory or central nervous system effects, genotoxicity, male reproductive toxicity, or immunotoxicity have been detected. The kidneys were the main target organ in mice and monkeys after 12 weeks of repeat dosing (weekly IV injections of casimersen and golodirsen) which is consistent with the renal excretion being the major elimination pathway for PMOs. No adverse effect were observed in mice using 960 mg/kg and 120 mg/kg of casimersen and golodirsen, and the maximum feasible dose for IV administration in monkeys was of 320 mg/kg for both PMOs. Because the potential target organ of toxicity (the kidney) can be monitored in the clinic, doses of 30 mg/kg casimersen or golodirsen are considered safe for once weekly IV infusions in DMD subjects with mutations amenable to exon 45 or exon 53 skipping. Additional non-clinical data for casimersen and golodirsen are described in the respective Investigator's Brochures.

Further, 30 mg/kg/wk golodirsen treatment in clinical trial 4053-101 resulted in a significant mean increase in dystrophin protein from baseline (N=25, p<0.001) at Week 48.

Due to the expected similarities among investigational PMOs for the treatment of subjects with DMD, a 30 mg/kg dose for eteplirsen, casimersen and golodirsen was selected for evaluation in this study.

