13.4 Safety Reporting and Meetings

Reports describing the status of the study will be prepared by the Principal Investigator's staff and sent to the DSMB before every meeting, every 6 months beginning with the first infusion, or at the DSMB's request.

A meeting (either by teleconference or webcast) with the DSMB will be scheduled prior to study initiation and reports will be submitted prior to a scheduled meeting for review by the DSMB.

Reports will include the following:

- A brief narrative of the study status, including the target enrollment, current and projected time to completing enrollment. Any significant events and/or difficulties should be briefly described in this narrative.
- A brief narrative for each participant describing gender, age, race and ethnicity and other relevant demographic characteristics. The narrative for each participant should briefly describe his/her study status (i.e., dose level, visit number, adverse event information);
- A timeline outlining the study progress relative to visit number for each participant, as well as time points for each SAE. A total for Adverse Events (AEs) for each participant should be included.
- A summary of AEs by severity levels;
- A listing of AE details grouped by participant;
- A listing of SAE details grouped by participant;
- A summary of TEAEs by System Organ Class, Preferred Term, and Maximum Severity
- A listing of deaths
- A summary of clinically significant laboratory test results

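### Under Section 11.3.4 an asymptomatic laboratory, ECG or ECHO adverse event is graded Mild whatever its size, even if study drug is stopped, so the severity tables can mislead for such events

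*Combined protocol and SAP*

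**What the plan says.** Section 11.3.4 sets one scale for everything: "The Investigator will assess the severity of all AEs as Mild, Moderate, or Severe, based on the following definitions". The lowest level is given as "Mild: The event does not interfere with the subject's usual activities". The middle level asks for some interference of that kind, and for nothing more. The top level adds a second condition: "The event prevents the subject from undertaking their usual activities and requires therapeutic intervention or cessation of the study treatment".

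Section 11.2.1 brings test findings into the adverse event definition: "Test abnormalities (laboratory tests, ECG, X-rays, etc.) that result in an alteration in medical care (diagnostic or therapeutic". A finding already present at Screening counts only if it worsens, or comes back after resolving.

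Section 6.2 reports that the kidney was the main target organ in mice and monkeys. It considers the casimersen and golodirsen dose safe on this ground: "Because the potential target organ of toxicity (the kidney) can be monitored in the clinic". The renal measures in Section 10.1.2 are laboratory tests (creatinine, BUN, cystatin C, urine protein).

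The grade is used in two tables in Section 11.3.9 (TEAEs by severity, and treatment-related TEAEs by severity) and two items in the DSMB report in Section 13.4. One is a summary of AEs by severity level. The other is "A summary of TEAEs by System Organ Class, Preferred Term, and Maximum Severity".

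**The concern.** Safety and tolerability is a primary objective (Section 5.1) and its analysis is descriptive (Section 14.3.2), so the severity tables are among the main safety outputs. The organ the protocol singles out is watched by laboratory tests, and a boy may feel nothing when such a value moves. Section 8.2.1 has no provision for altering the dose, so any response made through study drug would be interruption or cessation. The severity scale takes no account of either when activities are unaffected.

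At stake is the reading of those tables. A marked renal laboratory change that ended treatment and a trivial one that prompted a repeat test would carry the same lowest grade. A statement that all events were mild could then be true to the scale and still mislead about tolerability.

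**Working it through.** The plan states no figure on this point, so the check is to apply the three definitions literally. Cross the effect on usual activities (three levels) with whether the event requires therapeutic intervention or cessation of study drug (two levels):

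| Effect on usual activities | Intervention or cessation required? | Grade under 11.3.4 |
|---|---|---|
| None | No | Mild |
| None | Yes | Mild |
| Interferes | No | Moderate |
| Interferes | Yes | Moderate |
| Prevents | No | Not Severe; Moderate, since preventing activities is also interfering with them |
| Prevents | Yes | Severe |

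Of the 3 × 2 = 6 combinations, 2 are Mild, 3 Moderate and 1 Severe. The second criterion changes the grade only in the bottom pair of rows. In the top pair it changes nothing.

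Next, place a symptom-free laboratory, ECG or ECHO finding in the table.

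1. Is it an adverse event? Yes, under Section 11.2.1, if it altered care. Stopping drug is such an alteration.
2. Does the scale apply? Yes; Section 11.3.4 covers all AEs and gives no separate rule for test findings.
3. Which row? No effect on activities, cessation required: row two, Mild. The size of the abnormality does not enter any definition.

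Could *cessation* stand alone as a route to Severe? The sentence does not read that way. Cessation, like intervention, is something the event *requires*, and that whole clause is joined by *and* to the clause on preventing activities.

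Does another section correct the grade?

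- Section 10.1.2 sorts laboratory results into clinically significant or not, by whether care changed. This is yes or no, not a grade.
- Section 14.3.2.2 plans frequency tables of predefined abnormal changes, but gives no thresholds and no link to AE severity.
- Section 11.3.6 records the action taken with study drug, separately from severity.
- No laboratory toxicity grading appears anywhere in the documents.

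None of these changes what enters the severity tables.

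**The case against.** The strongest case on the other side is that nothing operational depends on this grade, and most of it stands. The reporting clocks in Section 11.5 run on seriousness, relatedness and expectedness. Section 11.3.4 itself separates severity from seriousness, and a medically important silent event may qualify as serious under Section 11.2.2. The DSMB consultation in Section 8.2.1 is triggered by interruption of two or more consecutive doses for an AE, at any grade.

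A reader might infer that the DSMB would not learn of a silent renal event. The documents do not support that. The reports in Section 13.4 also carry laboratory results judged clinically significant, AE and SAE details by participant, and a narrative for each boy. With about six subjects, a severity count is unlikely to hide a discontinuation.

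A reader might also infer that the protocol expects kidney toxicity. It does not say so: Section 6.2 speaks of a potential target organ from animal data and considers the dose safe, and Section 4.4 describes the expected risk as relatively low.

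Nor does the plan support a contrast such as 0/6 against 1/6 moderate or severe renal events. The event would be assumed, and Sections 11.3.9 and 14.3.2 tabulate by treatment group, whose sizes are not given.

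Finally, one might argue that the tables would be correct under their own definition, and that intensity and action taken are rightly kept apart. Both points are fair. The tables would be misleading rather than wrong, and letting cessation alone define Severe would merge two variables that the protocol records separately. What the objection does not answer is that activity is a poor measure of intensity for a finding the subject cannot feel, and the plan offers no other measure.

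**Conclusion.** The point holds as a limited one. By the literal text, no AE can be graded above Mild without interfering with usual activities. Every symptom-free laboratory, ECG or ECHO AE is therefore Mild, whatever its size and whatever was done about it. Two TEAE tables and two DSMB summaries would be misleading for such events. Awareness of the events, expedited reporting and DSMB triggers are not affected.

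The scale is not purely an activity scale, since Severe has a second condition; that condition simply cannot lift an event with no effect on activities. In the other direction, an event that prevents activities but needs no intervention or cessation falls to Moderate, so it is still counted.

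The conclusion assumes that investigators apply the definitions as written and that the CRF Completion Guidelines, which are not part of the documents, add no rule for test findings. If investigators used judgement instead, grades would depend on the rater, which is also a reason to fix the wording. How often such events would occur cannot be derived from the documents.

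**What to change.** In Section 11.3.4:

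- Keep the usual-activities wording for symptomatic events.
- For AEs that are test abnormalities, have the Investigator grade by the size of the abnormality on one established toxicity scale, named in the protocol and mapped to Mild, Moderate and Severe. Where the value was already abnormal at Screening, grade relative to baseline, in line with Section 11.2.1.
- State that *asymptomatic* does not by itself mean Mild.

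Keep action taken (Section 11.3.6) as its own variable, and show treatment interruption or discontinuation alongside the severity tables in Section 11.3.9 and the summaries in Section 13.4.

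The cost is a few lines in the protocol and a short mapping in the CRF guidelines. The measurements are already collected. The downside is that a few more events may be graded moderate or severe. No dose, stopping or other clinical management rule changes.
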